1. Difference in total HEI score between groups during the post-intervention period	Automated Self-Administered 24-hour (ASA24 [®]) survey-derived total HEI-2015* score; score based on two diet recalls per assessment period, collected via web-based survey (ASA24 Version 2022 or later)

CGM Initiation in People with T2D

*Survey-derived HEI-2015 scores may be replaced with a newer scoring option if both scoring and analysis code become available

Exploratory Outcomes

Outcome	Assessment Method

1. Change in other CGM-derived core metrics from baseline to post-intervention; including as described by the 24-hour period, daytime period (6AM to 11:59PM), and nighttime period (12AM to 5:59PM):
 
 • number of days CGM device is worn • % time CGM sensor is active • mean sensor glucose mg/dL • % coefficient of variation • glucose management indicator (GMI) • % time above >250 mg/dL • % time above >180 mg/dL • % time below <70 mg/dL • % time below <54 mg/dL 	
See CGM-related outcome measures described above

2. Other CGM-derived metrics:
 
 • Change in % time in tight range (% time with glucose 70-140 mg/dL) from baseline to post-intervention • % of participants reaching CGM-derived consensus targets during post-intervention²⁶ 
 ○ % reaching >70% TIR (% time with glucose 70-180 mg/dL) ○ % reaching ≥5% improvement in TIR (% time with glucose 70-180 mg/dL) compared to baseline ○ % reaching >70% time TIR (% time with glucose 70-180 mg/dL) and reaching a ≥5% improvement in time in range compared to baseline 	
See CGM-related outcome measures described above

3. Describe HEI component scores by group during the post-intervention period
	
ASA24 survey-derived HEI-2015* component scores; scores based on two diet recalls per assessment period, collected via web-based survey (ASA24 Version 2022 or later)

4. Change in additional nutrition metrics from baseline to post-intervention
 
 • total energy intake • macronutrients and fiber 	
ASA24 survey-derived values based on two diet recalls per assessment period, collected via web-based survey (Version 2022 or later)

CGM Initiation in People with T2D

 select micronutrients 	

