Phase 1: This is a non-pivotal, randomized, parallel group, two-arm, prospective study. This 60-day pilot study will evaluate the effect of a NFA versus a SDA during CGM initiation in people with T2D. It is hypothesized that the NFA arm will see greater improvement in TIR than the SDA arm, due to the potential for dietary improvements that come from the use of the NFA and its associated nutrition-focused CGM initiation materials. To test this hypothesis, participants will be randomized 1:1 to either the NFA or the SDA arm.

The intervention begins on Day 0, which is the day the G7 sensor is paired with apps on the participant's personal cell phone. The intervention follows participants for approximately 50 days, which includes an up to 10-day CGM wear period that is part of the post-intervention assessment (approximately Days 40 to 50). During the final 10 days, the participant is instructed to continue using the CGM device in accordance with the guidance provided based on randomization arm.

Phase 2: The follow-up period is designed to evaluate the impact of discontinuing CGM use. The follow-up assessment period begins the day after the Phase 1 post-intervention period ends, approximately Day 51. The follow-up assessment period passively follows participants for 4 months, which includes the 10-day blinded CGM wear period from approximately Day 170 to 180.

On approximately Day 170, participants will return to the clinic to initiate a Dexcom G7 sensor paired with a physically blinded Dexcom receiver and to complete additional assessments. It is hypothesized that glycemic improvements made during the Phase 1 intervention will be reduced during the Phase 2 follow-up due to the removal of real-time glucose feedback and other associated CGM data.

14. Participant Population

Phase 1: To be eligible for the Phase 1 study intervention, all participants must meet the following inclusion and exclusion criteria.

Inclusion Criteria

- Adults ≥ 18 years of age
- T2D diagnosis
- HbA1c 7.0%-10.0% at the time of screening. If a participant has an investigator-approved HbA1c test that was lab-analyzed within the sponsoring institution and that is within 7 days of the screening date, this value may be used.
- Taking no diabetes medication or taking stable-dose diabetes medication(s) for at least 30 days; willing to maintain stable diabetes medication regimen for the duration of the study

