	Mild (plasma glucose >250 mg/dl)	Moderate (plasma glucose >250 mg/dl)	Severe (plasma glucose >250 mg/dl)	Plasma glucose >600 mg/dl
Arterial pH	7.25–7.30	7.00 to <7.24	<7.00	>7.30
Serum bicarbonate (mEq/l)	15–18	10 to <15	<10	>18
Urine ketone*	Positive	Positive	Positive	Small
Serum ketone*	Positive	Positive	Positive	Small
Effective serum osmolality†	Variable	Variable	Variable	>320 mOsm/kg
Anion gap‡	>10	>12	>12	Variable
Mental status	Alert	Alert/drowsy	Stupor/coma	Stupor/coma

*Nitroprusside reaction method. †Effective serum osmolality: 2[measured Na⁺ (mEq/l)] + glucose (mg/dl)/18. ‡Anion gap: (Na⁺) – [(Cl⁻ + HCO₃⁻) (mEq/l)]. (Data adapted from ref. 13.)

Table taken from Kitabchi et al⁴³

Only reportable AEs and all SAEs will be recorded within an adverse event log with a description including the nature of the event, the date and time of onset and/or frequency, determination of non-serious versus serious, intensity (mild, moderate, severe), duration of the event, relationship to the intervention, the expectedness of the event, and outcome of the event. All reportable AEs and all SAEs will be reviewed and confirmed by a delegated medical doctor or equivalent. All AEs and SAEs must be resolved or deemed stable by a delegated medical doctor or equivalent before a participant completes or withdraws from the study.

Delegated study staff will report all reportable AEs, SAEs, and UPIRTSOs to the IRB in accordance with IRB policies.

22. Study Suspension or Discontinuation

This study will be suspended or stopped prior to completion if information becomes available during the study that indicates as such, this may include information related to adverse events or the potential for adverse events. The study may also be suspended or stopped prior to completion if recruitment

CGM Initiation in People with T2D

challenges or retention issues will impact the ability to properly analyze defined endpoints or for other reasons determined by the Investigator.

23. Statistical Considerations

Phase 1 Statistical Hypotheses

Primary Endpoint: Change in CGM-derived TIR (% time with glucose 70-180 mg/dL) from baseline to post-intervention.

Hypothesis (alternative): Participants randomized to a nutrition-focused approach (NFA) will show a larger increase in CGM-derived TIR from baseline to post-intervention than participants randomized to a self-directed approach (SDA).

Secondary Endpoint: Difference in total HEI score between groups during the post-intervention period.

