Hypothesis (alternative): Participants randomized to a nutrition-focused approach (NFA) will show a higher total HEI score during the post-intervention than participants randomized to a self-directed approach (SDA).

Phase 2 Statistical Hypothesis

Primary Endpoint: Change in CGM-derived TIR (% time with glucose 70-180 mg/dL) from post-intervention to follow-up

Hypothesis (alternative): Participants will show a reduction in CGM-derived TIR from post-intervention to follow-up.

Sample Size Determination

Phase 1 of the study will enroll at least N=132 participants with the expectation for an analytic sample size of N=120. This sample size is based on the N needed to adequately power the primary hypothesis with a realistic and clinically meaningful effect size for % TIR. Specifically, existing research on CGM initiation in people with T2D shows mean TIR of 59% with SD of 25% after intervention.

An analytic sample size N=60 participants per arm has 80% power ($\alpha=.05$, two-sided) to detect an absolute differential change by study arm (i.e., more improvement in the NFA than SDA arm) of 12.9% from baseline to post-intervention (day 50). Justification to support a 12.9% difference in TIR requires converting A1c study data to TIR. The Mobile study showed a 0.4% decrease in A1c after CGM initiation in people with T2D using insulin; we expect a slightly smaller, 0.3%, improvement in our non-insulin using population. An eight-week nutrition intervention study showed a 1.2% decrease in A1c with the DASH diet; we expect a more conservative, 0.7%, improvement (in the NFA arm).

Using the A1c to TIR conversion (0.5% A1c reduction equals 10% TIR increase) suggests a 14% increase (difference) in TIR.

To account for approximately 10% attrition, the enrollment target will be set at N=66 per arm; total N=132.

CGM Initiation in People with T2D

The Phase 2 sample is dependent on the number of participants that complete Phase 1 and continue through the Phase 2 follow-up assessment period. It is expected that 90% of those completing Phase 1 (n=54/arm) will complete Phase 2 and have CGM data at follow-up. It is expected that 85% of those completing Phase 1 (n=51/arm) will complete Phase 2, have at least 7 days of CGM data at follow-up, refrain from CGM use during the follow-up period, and have no glucose-lowering medication changes during the follow-up period.

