With an expected sample size of n=54 per arm for the intention to treat (ITT) sample in Phase 2, the primary analysis has 80% power ($\alpha=.05$, two-sided) to detect an absolute change for pooled study arms of 0.27 standard deviation units of change in TIR from the end of the intervention to follow-up. For within-arm tests of change in this sample the primary analysis has 80% power ($\alpha=.05$, two-sided) to detect an absolute change within a study arm of 0.39 standard deviation units of change in TIR from the end of the intervention to follow-up.

Populations for Analysis

The analysis for Phase 1 will follow a modified intention to treat perspective, with an analysis of CGM metrics that includes only participants with at least seven days of CGM data at both baseline (approximately day -11 to -1) and post-intervention (approximately day 40 to 50).

The analysis for Phase 2 will follow a modified intention to treat perspective, with an analysis of CGM metrics that includes only participants with at least seven days of CGM data at both post-intervention and follow-up. This sample is utilized to assess the effect of discontinuation of CGM utilized in phase 1. A per-protocol (PP) analytic sample will consist of participants with at least seven days of CGM data at both post-intervention and follow-up who did not use CGM, and who did not require changes to glucose-lowering medications during the follow-up period. This PP sample is utilized to assess the effect of discontinuation on patients not utilizing CGM and having no medication adjustments during the follow-up period.

General Approach for Statistical Analyses in Phase 1

Baseline characteristics of study participants will be summarized with mean and standard deviation for interval data and proportions for categorical data. For analyses that do not concern total HEI or HEI component scores, the analytic models will utilize general and generalized linear mixed model repeated measures analysis to estimate differential change by study arm from baseline to post-intervention period. The link function and error distribution selected for each model will be based on the distribution of the endpoint. Each model will include fixed effects for study arm, time, their interaction, variables used in stratification, and a random intercept for patient. Each model will report the model-derived estimate (and 95% confidence interval) for the endpoint by study arm and by time period (baseline, day 50).

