The key analytic test for the primary endpoint will be based on planned contrasts reflecting the interaction of study arm and time period and will report and test model-derived estimates of differential change by study arm along with 95% confidence intervals. For the primary outcome, statistical comparisons will be made between and within arms and for study arm by time interaction with significance assessed at $p < 0.05$. A final Statistical Analysis Plan will specify further analytic detail and inclusion of any additional covariates.

For analyses of total HEI score and HEI component scores, mean scores will be computed separately at

CGM Initiation in People with T2D

each time point (pre-intervention, post-intervention) and for each study group. Confidence intervals for means will be based on a Monte Carlo approach implemented with code developed for the HEI-2015 utilizing a population ratio method appropriate for ASA24 data (e.g. HEI2015_ASA24-2016_MC_PopulationScore.sas). Note: if additional versions of HEI scoring, coding, and analysis become available, these may be used (e.g. HEI-2022).

Analysis of Primary Endpoint

The analysis of the primary endpoint tests whether patients randomized to a nutrition-focused approach (NFA) will have a larger increase in CGM-derived TIR from baseline to post-intervention than patients randomized to a self-directed approach (SDA). A general linear mixed model repeated measures analysis will estimate differential change by study arm from baseline to post-intervention period in TIR. The analytic model will include fixed effects for study arm, time, their interaction, variables used in stratification, and a random intercept for patient. A final Statistical Analysis Plan will specify any additional covariates to be included in the model.

Analysis of Secondary Endpoint

The analysis of the secondary endpoint tests whether patients randomized to a nutrition-focused approach (NFA) will have higher total HEI score at post-intervention than patients randomized to a self-directed approach (SDA). Mean total HEI scores and 95% confidence intervals computed for each study group will be compared to understand study group differences.

Safety Analysis

The trial does not have formal safety endpoints or formal rules or statistical guidance on stopping due to safety concerns. The review and reporting of AEs and SAEs is detailed in the Assessment of Safety and Safety Reporting sections.

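### The only Phase 1 secondary endpoint, the between-arm difference in total HEI, is called a test, but the plan gives no interval, test, alpha or decision rule for that difference

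*Combined protocol and SAP*

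**What the plan says.** Section 11 (Secondary Outcome) lists one Phase 1 secondary outcome: "Difference in total HEI score between groups during the post-intervention period". Section 23, Phase 1 Statistical Hypotheses, repeats it and attaches a formal alternative, that NFA participants will score higher than SDA participants. Section 23, Analysis of Secondary Endpoint, says the analysis tests this, and then gives the whole method in one sentence: "Mean total HEI scores and 95% confidence intervals computed for each study group will be compared to understand study group differences".

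The intervals come from the General Approach for Phase 1, which computes a mean for each group and time point with a Monte Carlo interval for that mean, using the population ratio method.

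The surrounding text does not supply the missing comparison:

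- **Mixed models.** These exclude HEI: "For analyses that do not concern total HEI or HEI component scores, the analytic models will utilize general and generalized linear mixed model".
- **Significance criterion.** The 0.05 level is tied to one endpoint: "For the primary outcome, statistical comparisons will be made between and within arms".
- **Post-only models.** Arm-effect models without a time term are offered for some exploratory analyses only.
- **Component scores.** The exploratory outcome in Section 11 is "Describe HEI component scores by group during the post-intervention period", and its analysis text in Section 23 is nearly the same as that for total HEI.
- **Final SAP.** The General Approach promises more detail in a final SAP, in a sentence that follows the primary-outcome text and does not mention HEI. The later promise about arm comparisons is limited to exploratory endpoints.

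**The concern.** An endpoint with a stated hypothesis is given the same treatment as one that is only to be described. The hierarchy is also inverted: exploratory endpoints under the mixed-model framework get a tested arm-by-time contrast, while the sole secondary endpoint gets no defined test.

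An interval for each arm's mean answers a question about that arm. A claim about the difference needs the standard error of the difference, and comparing two arm-specific 95% intervals by eye is not a 5% test of it. Since the plan fixes no reading, one can be chosen once the results are known, and the error can run in either direction.

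Section 13 expects NFA to improve TIR through better diet. The total HEI comparison is the planned evidence on that step, so its interpretation should not depend on a later choice.

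**Working it through.** **The plan's own Phase 1 figure.** The only Phase 1 design calculation is for TIR: 60 per arm, difference 12.9, SD 25, two-sided alpha 0.05, stated power 80%.

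- Standard error of the difference: 25 × √(2/60) = 4.564.
- Standardised effect: 12.9 / 4.564 = 2.826.
- Normal-approximation power: Φ(2.826 − 1.960) = 0.807. With a noncentral t on 118 degrees of freedom it is 0.800.

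The stated figure reproduces. The documents give no SD, target difference, alpha or power for total HEI.

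**What follows from an unstated reading rule.** The assumptions are mine: independent arms, approximately normal arm means, and standard error s in each arm. The difference then has standard error s√2. The benchmark is a direct two-sided 5% test, |z| > 1.960, where z = difference / (s√2). The mean of z is 1.960 + 0.842 = 2.802 when direct power is 80%, and 1.960 + 1.282 = 3.242 when it is 90%.

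*Reading (a): the two 95% intervals do not overlap.* This needs |difference| > 2 × 1.960 × s, that is |z| > 1.960 × √2 = 2.772.

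- Size: 2 × (1 − Φ(2.772)) = 0.0056.
- Power where the direct test has 80%: Φ(2.802 − 2.772) = 0.512.
- Power where the direct test has 90%: Φ(3.242 − 2.772) = 0.681.

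*Reading (b): one arm's mean lies outside the other arm's interval.* This needs |difference| > 1.960 × s, that is |z| > 1.960 / √2 = 1.386.

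- Size: 2 × (1 − Φ(1.386)) = 0.166.
- Power where the direct test has 80%: Φ(2.802 − 1.386) = 0.922.

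*Disagreement.* The readings conflict when 1.386 < |z| < 2.772, which is a direct p-value between 0.166 and 0.006.

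- No true difference: 0.1658 − 0.0056 = 0.160.
- Direct power 80%: 0.922 − 0.512 = 0.410. Of this, 0.288 is where the direct test is significant but the intervals overlap, and 0.122 is where it is not significant but one mean lies outside the other interval.

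**Unequal standard errors** (assumed ratio r from 1 to 2). The non-overlap cut-off is 1.960 × (1 + r) / √(1 + r²). Reading (b) now splits: either mean outside the other interval has cut-off 1.960 / √(1 + r²), and both means outside has cut-off 1.960 × r / √(1 + r²).

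| SE ratio | Size, (a) | Power, (a), at 80% direct | Size, (b) either | Size, (b) both |
|---|---|---|---|---|
| 1 | 0.0056 | 0.512 | 0.166 | 0.166 |
| 1.5 | 0.0066 | 0.533 | 0.277 | 0.103 |
| 2 | 0.0085 | 0.568 | 0.381 | 0.080 |

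Over these ratios, disagreement between (a) and (b) runs from about 7% to 37% with no true difference and from about 28% to 42% at 80% direct power.

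**The case against.** Four points deserve weight.

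- **Deferral.** The promise of more detail sits under the same General Approach heading as the HEI paragraph, so a final SAP may fill the gap. That is possible, but the sentence does not mention the HEI difference, and it leaves in place a stated method that does not deliver the stated test.
- **Not purely descriptive.** A Monte Carlo 95% interval for an arm mean is an inferential statement. This is correct. The gap concerns the difference only.
- **Illustrative figures.** The plan names neither reading, the 80% reference power for HEI is assumed, and the same arithmetic fits any two-arm comparison. This stands: the figures show why a rule must be stated, not that a number in the plan is wrong. The equal-SE values for reading (b) also move a good deal when the standard errors differ, which strengthens the case for naming a rule.
- **Pilot status.** Section 13 says "This is a non-pivotal, randomized, parallel group, two-arm, prospective study", and the sample size is justified on TIR alone. A descriptive HEI comparison could be acceptable here. The hypothesis and the secondary-endpoint text, however, present it as a test.

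**Conclusion.** The concern holds. The text announces a test of the total HEI difference and provides no interval, test, alpha, sidedness or decision rule for it. Depending on how the two arm intervals are read, the type I error at equal standard errors could be 0.6% or 16.6% against a 5% benchmark. The non-overlap reading would turn 80% direct power into 51%. These sizes rest on independent arms, approximate normality and the stated SE ratios. The finding itself rests only on the wording.

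The primary TIR analysis is unaffected. This should be corrected before results are seen, but it is not a fatal flaw in a pilot.

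**What to change.** In Section 23, Analysis of Secondary Endpoint, and in the final SAP, do one of the following.

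1. **Keep the test.** Prespecify the NFA minus SDA difference in post-intervention total HEI with its own 95% confidence interval and a two-sided 0.05 test, matching the convention used for TIR. One simple form is z = difference / √(SE₁² + SE₂²), with each arm's standard error taken from the planned Monte Carlo run, or from the 95% interval width divided by 3.92 (2 × 1.96) if the interval is roughly symmetric. An interval from the Monte Carlo or bootstrap distribution of the difference would serve equally well, provided it is named in advance. State that overlap or visual comparison of arm-specific intervals will not be used for inference.
2. **Make it descriptive.** Reword the hypothesis and the secondary-endpoint text so that they describe rather than test. Still report the difference with its 95% interval, and make no claim of significance.

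Component scores can stay descriptive under either option. The cost is one or two sentences and one calculation from arm-level results already planned, with no new data and no change in sample size.

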Once at least seven days of baseline G7 sensor data are confirmed, participants will receive their randomization assignment to either the NFA or the SDA arm.

Given that enrolling participants takes several months to complete, randomly permuted blocks of size two, four, and six will be used to ensure that participants are assigned to the NFA and SDA arms in approximately equal proportions over time. Randomization will be carried out within strata defined by participant's most recently available HbA1c $>8.5\%$ vs. $\leq 8.5\%$. The participant randomization schedule will be generated by the study statistician using a random number generator. Participants will remain in their assigned study arm throughout the intervention.

Blinding procedures are not described since blinding is not possible in a study comparing two different instructional approaches; the study staff and participants will know what type of instruction they give or receive. However, study participants will not know the details of the type of education provided to the other study arm (i.e. participants in the self-directed approach arm will not know the other arm is receiving a nutrition-focused approach and vice-versa).

Phase 1: Intervention

The intervention compares the effects of two different approaches used during CGM initiation, the NFA or SDA. For both arms, the intervention will include one in-person and one remote study appointment. All care and instruction will be provided by IDC research staff serving as interventionists. Intervention study staff will receive verbal training and written materials describing how to deliver the NFA and SDA; and checklists will be used to ensure consistent delivery among study staff and within each study arm.

On study Day 0, participants who have met all eligibility criteria and who have at least seven days of blinded CGM data will receive Dexcom G7 systems that will be paired with apps on their personal cell phone. Study staff will assist the participant in applying the G7 sensor, as needed. All participants will be instructed to wear and use the G7 and the associated phone apps continuously throughout the intervention, including changing out the sensors every 10 days or as needed. Intervention duration is expected to last approximately 50 days.

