General Approach for Statistical Analyses in Phase 2

The general approach for the analysis of Phase 2 will follow the approach used for Phase 1, but with modifications to the contrasts computed. The analytic models will utilize general and generalized linear mixed model repeated measures analysis and include fixed effects for study arm, time, their interaction, variables used in stratification, and a random intercept for patient. Each model will report the model-derived estimate (and 95% confidence interval) for the endpoint by study arm and by time period. The link function and error distribution selected for each model will be based on the distribution of the endpoint. Analysis will be conducted with both the modified ITT sample for Phase 2 and the PP sample.

The key analytic test for the primary endpoint will be based on planned contrasts (effect slices) reflecting the change from the end of the intervention period to the follow-up period, with study arm data pooled. Model-derived estimates of change across these two periods will be reported along with 95% confidence intervals. For the primary outcome, effect slices will also be tested for within-study arm change from the end of the intervention period to the follow-up period. A final Statistical Analysis Plan will specify further analytic detail and inclusion of any additional covariates.

CGM Initiation in People with T2D

Planned Interim Analysis

Not applicable

Sub-Group Analyses

There are no planned sub-group analyses or analyses to assess heterogeneity of treatment effects.

Analysis of Exploratory Endpoints in Phase 1

Exploratory endpoints are listed in the section Phase 1 Study Outcome Measures: Exploratory Outcomes.

Analysis of exploratory endpoints will follow the analytic framework used for the primary endpoint and will report model-derived estimates and statistical testing of the interaction contrast. However, the test of this interaction is considered hypothesis-generating and is not necessarily powered adequately. Some exploratory analyses will be post-only analyses using the same analytic framework but will include only fixed effects for study arm and stratification factors, but not an effect for time or their interaction. There will be no control for multiple testing in exploratory analyses. In sensitivity analysis, models will adjust for key prognostic factors selected a-priori.

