Analysis of HEI component scores will include computing mean component scores and 95% confidence intervals for each study group; these will be compared to understand study group differences. Radar plots will be used to display differences. Summaries of intervention fidelity and potential behavioral mechanisms will utilize descriptive statistics computed within each study group.

Linear regression and Pearson or Spearman correlations will assess associations between TIR and HEI, HbA1c and HEI, participant perception of diet quality and calculated total HEI score. Additional analysis specifications involving study arm comparisons for exploratory endpoints and detailed specifications of other exploratory analyses will be described in a final Statistical Analysis Plan.

Analysis of Exploratory Endpoints in Phase 2

Exploratory endpoints are listed in the section Phase 2 Study Outcome Measures: Exploratory Outcomes.

Analysis of exploratory endpoints will follow the analytic framework for Phase 2 used for the primary endpoint and will report model-derived estimates and statistical testing of the change from the end of the intervention to follow-up period in the pooled study arms and within each study arm via pre-specified contrasts. Some exploratory analyses will be post-only analyses using the same analytic framework but will include only fixed effects for study arm and stratification factors, but not an effect for time. There will be no control for multiple testing in exploratory analyses. In sensitivity analysis, models will adjust for key prognostic factors selected a-priori.

Analysis of HEI component scores will include computing mean component scores and 95% confidence intervals for each study group at follow-up. Summaries of potential behavioral mechanisms will utilize descriptive statistics computed within each study group.

24. Data Collection and Management

Source data for the study will be collected verbally, physically, or electronically direct from the participant, from the participant's EMR, from the participant's G7 CGM system and the Clarity website, from web-based platforms where data is entered directly by the participant or with assistance of study staff (e.g. ASA24, DietID, REDCap, etc).

Study staff will record data in accordance with the UNITE Study MOP (UNITE MOP). Study data will be stored as follows:

- on paper case report forms
- in the participant EMR

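### The main Phase 1 post-only exploratory models leave out baseline values already collected, which costs precision, most plausibly for the time-in-range target outcomes

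*Combined protocol and SAP*

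**What the plan says.** The rule is in section 23, Analysis of Exploratory Endpoints in Phase 1. The default exploratory analysis there is the arm-by-time mixed model of the primary endpoint. The plan then adds: "Some exploratory analyses will be post-only analyses using the same analytic framework", and these models "will include only fixed effects for study arm and stratification factors, but not an effect for time or their interaction". The matching Phase 2 paragraph repeats the rule: "will include only fixed effects for study arm and stratification factors, but not an effect for time".

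Other parts of the document that bear on it:

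- **Stratification** (section 15, Randomization). "Randomization will be carried out within strata defined by" HbA1c above 8.5% versus at or below 8.5%. This is the only stratification factor.
- **Baseline data** (section 23, Populations for Analysis). The Phase 1 CGM analysis "includes only participants with at least seven days of CGM data at both baseline" and post-intervention, so baseline TIR exists for every analysed participant.
- **Outcomes** (section 11, Exploratory Outcomes, item 2). The plan will report the percentage "of participants reaching CGM-derived consensus targets during post-intervention". The targets are TIR above 70%, an improvement of at least 5%, and both together.
- **Sensitivity analysis** (same paragraph as the rule). "In sensitivity analysis, models will adjust for key prognostic factors selected a-priori". No factor is named.
- **Power** (same paragraph). For the exploratory arm-by-time contrast, "the test of this interaction is considered hypothesis-generating and is not necessarily powered adequately".

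**The concern.** A participant's own starting TIR is likely to be a strong predictor of whether they end above a TIR threshold. The main post-only model replaces it with a two-level HbA1c stratum, which can carry only part of the information.

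A simple calculation shows what is discarded. Assume a baseline mean of 50, a control post-intervention mean of 59, SD 25 at both times and a correlation of 0.5.

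- A control participant starting at 30% has expected post-intervention TIR 59 + 0.5 × (30 − 50) = 49. The residual SD is 25 × √(1 − 0.25) = 21.7, so the chance of exceeding 70% is about 17%.
- A control participant starting at 68% has expected TIR 59 + 0.5 × (68 − 50) = 68, and a chance of about 46%.

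Ignoring such differences leaves the arm comparison noisier than it need be and exposed to chance imbalance in baseline TIR. The continuous primary analysis brings the baseline measurement in through the repeated-measures model. The dichotomised version of the same measure would not.

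**Working it through.** **1. Which outcomes are post-only?** The plan does not list them, so work through the Phase 1 exploratory outcomes in section 11.

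- Items 1 and 4 to 7, and the tight-range part of item 2, are changes from baseline, so the arm-by-time model fits them.
- Item 3 (HEI components) has its own Monte Carlo method.
- Items 8 and 9 (fidelity, behavioural mechanisms) are summarised descriptively.
- The consensus targets in item 2 remain. Two of the three are defined relative to baseline and so have no baseline counterpart to enter a repeated-measures model. The share above 70% TIR could be fitted either way, but its wording points to post-only.

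This is an inference from the outcome definitions.

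**2. Reproduce the plan's own figure.** Sample Size Determination gives 60 per arm, 80% power, two-sided α = 0.05, 12.9 points and SD 25.

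- Normal approximation: n = 2 × (1.960 + 0.842)² × (25/12.9)² = 59 per arm.
- Two-sample t-test: n = 59.9, power 80.0% at 60 per arm, detectable difference 12.89.

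The figure reproduces. If SD 25 applies both to a single-time value and to the change, then 2 × 25² × (1 − ρ) = 25², which gives ρ = 0.5. The plan states no correlation.

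**3. Unadjusted power for the share above 70% TIR.** Take the plan's mean of 59 and SD of 25 for control, shifted by 12.9 for the nutrition-focused arm.

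- Control: P(Z > (70 − 59)/25) = P(Z > 0.44) = 33.0%.
- Nutrition-focused: P(Z > (70 − 71.9)/25) = P(Z > −0.076) = 53.0%.
- Two-proportion power at 60 per arm: 60.3%.

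**4. Add baseline TIR.** The simulation used 3,000 trials per row, 60 per arm, allocation balanced within stratum, and likelihood-ratio tests for arm in a logistic model. Assumptions not in the documents: the baseline-to-post correlation ρ, about 30% of participants in the high-HbA1c stratum, the HbA1c–TIR correlation r, and TIR truncated to 0–100.

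| r | ρ | Arm + stratum | + baseline TIR | Gain (points) |
|---|---|---|---|---|
| −0.6 | 0 | 62.5% | 62.3% | none |
| −0.6 | 0.3 | 64.0% | 64.7% | 0.7 |
| −0.6 | 0.5 | 62.4% | 67.7% | 5.3 |
| −0.6 | 0.7 | 64.4% | 77.8% | 13.4 |
| −0.6 | 0.8 | 67.2% | 85.4% | 18.2 |
| 0 | 0.5 | 62.1% | 68.7% | 6.6 |
| 0 | 0.7 | 61.2% | 76.7% | 15.5 |
| −0.8 | 0.5 | 63.9% | 67.9% | 4.0 |
| −0.8 | 0.7 | 66.9% | 78.4% | 11.5 |

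A second set-up, with baseline mean 50 and a noisy binary stratum, gave 64.1% → 67.3% at ρ = 0.5 (3.2 points) and 65.3% → 74.7% at ρ = 0.7 (9.4 points).

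The simulation standard error of each power figure is about √(0.65 × 0.35/3000) = 0.9 points, so the 0.7-point gain at ρ = 0.3 cannot be told from zero. Even at r = −0.8 the HbA1c stratum does not replace baseline TIR.

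**5. Type I error.** In the first set-up (r = −0.6) rejection under no effect was 4.8–5.9% without baseline TIR and 5.3–6.0% with it. In the second it was 4.9% and 5.3%. Slight small-sample excess in the test cannot account for the gains at ρ = 0.5 and above.

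**6. The other two targets.** A smaller run of 1,500 trials per cell (baseline mean 50, r = −0.6) gave the following power at ρ = 0.5 and 0.7.

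- Improvement of at least 5%: 57% → 65% and 76% → 81%.
- Both targets, with baseline TIR and its square in the model: 64% → 68% and 73% → 78%.

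Baseline therefore still helps when the target is already defined relative to it.

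**The case against.** Several points on the other side have force.

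- **Adjustment is already planned as a sensitivity analysis.** The same paragraph provides for it, and baseline TIR is an obvious candidate. But no factor is named, and the main model stays as stated.
- **The rule may not be closed.** The post-only models share the primary framework, for which a final SAP may specify additional covariates, and further exploratory detail is also deferred to that SAP. The wording can be read as describing which repeated-measures terms drop out. That reading is possible, but the sentence as written restricts the fixed effects to arm and stratification factors. The deferral is an argument for settling the matter in the SAP.
- **The analyses are exploratory.** No power is claimed for them, multiplicity is uncontrolled, and continuous TIR is already analysed with its baseline. This stands, and it makes the point a minor one.
- **The size depends on assumptions.** This also stands. At the correlation implied by the plan's use of SD 25 the gain is modest, and at 0.3 it disappears.

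A reader might go further in three ways that the documents do not support.

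- *The arm comparison is biased or invalid.* It is not: allocation is randomised within HbA1c strata, and simulated type I error without baseline TIR is close to nominal.
- *The plan assigns the share above 70% TIR to this model.* It says only that some analyses are post-only, and the assignment is inferred from the outcome's wording.
- *The same loss applies in Phase 2.* Nothing was computed for Phase 2, where the tests of change are pooled or within arm.

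**Conclusion.** The point holds as a minor, inexpensive improvement. The main Phase 1 post-only models omit a baseline value that is already in hand, and the TIR targets are the natural place where this matters. The loss is one of precision.

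For the share above 70% TIR, with 60 per arm and a 12.9-point shift, adding baseline TIR is worth about 3 to 7 points of power if the baseline-to-post correlation is 0.5. It is worth about 10 to 15 points at 0.7 (individual rows 9.4 to 15.5), and negligibly little at 0.3 or below. These figures rest on an assumed correlation, an assumed HbA1c–TIR relation and stratum split, and the inference that this outcome is analysed post-only. The point does not touch items with no baseline or the HEI scores.

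**What to change.** In the final SAP:

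1. List the exploratory endpoints that will be analysed post-only.
2. For each one whose underlying measure has a baseline, add the continuous pre-randomisation value to arm and HbA1c stratum. For the TIR targets this is baseline TIR. For the combined target, allow a squared term, because neither very low nor very high starters can easily meet both parts.
3. For binary outcomes, report a standardised risk difference with its confidence interval: predict each participant's risk under each arm and average the differences. Adding a covariate changes the meaning of the odds ratio, and this keeps the reported effect marginal.
4. Keep arm-plus-stratum models only where no baseline exists.
5. If the rule is extended to Phase 2 arm comparisons, use the pre-randomisation baseline. The post-intervention value is measured after the arms have diverged, and adjusting for it could remove part of the arm effect.

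Naming the sensitivity-analysis factors at the same time would remove the remaining ambiguity. The cost is SAP wording and one covariate (plus its square for the combined target), with no new data. It should be settled before outcome data are examined, since adding baseline later would look post hoc.
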